**Table A6 Supervised Exercise Therapy Compliance Measurement**

Centre	Sessions per week	Months	total session	50%
*Imperial College Healthcare	1	6	24	12
North Bristol	2	3	24	12
Hull and East Yorkshire Hospitals	3	3	36	18
University Hospital Southampton	1	2	8	4
Dorset County Hospital	1	2	8	4
Royal Bournemouth & Christchurch Hospital	1	3	12	6

\*Imperial SET classes typically last 6 months so extra classes beyond 3 months are entered under unscheduled visit

### 13.3.3 NMES Compliance Measurement

For NMES, we know that the patients are recommended to use the device for 30 minutes a day for 12 weeks, for a total of 2520 minutes. Therefore, we will classify a patient as a complier if they use the NMES device at least 75% of the recommended time for 12 weeks.

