### **5.5.4. Neuromuscular electrical stimulation device**

Revitive IX is a disc shaped, footplate device used in a seated position with the soles of both feet in contact with the conductive footpads. The user is able to alter the stimulation intensity until there are visible strong yet comfortable calf muscle contractions and associated heel-toe raises.

Imperial Clinical Trials Unit	NESIC Clinical Study Protocol V6.0 24/03/2020	Form Number CR001A-T
-------------------------------	---	-------------------------

The groups randomised to the NMES device, will be familiarised with the device by asking them to place the soles of both feet onto the respective footpads. The IsoRocker will be enabled throughout the study period. Baseline sensory and motor thresholds will be established and noted. The sensory (perception) and motor thresholds will be established by systematically varying the stimulation intensity with steps of  $\pm 1\%$  maximal output whilst the participant provides verbal sensory feedback. The minimal intensity, which the participant is able to clearly feel, will be recorded as the perception threshold, and that producing visible muscle twitches as the motor threshold. The stimulation intensity for the main interventions will be adjusted to produce visible strong but non-painful contraction of the lower limb musculature based on the individual suprathreshold. Participants will be instructed to use the device to as close a stimulation intensity to this suprathreshold level without the experience being uncomfortable. Participants will be made aware that they may need to increase the intensity over time to compensate for habituation (familiarisation with the electrical muscle stimulation).

Patients will be advised to complete at least one pre-programmed 30-minute session of NMES daily, to a maximum of 6 sessions and record usage in the compliance diary. Where patients are also diagnosed with diabetes, a minimum usage of two (2) x 30 minute sessions per day is recommended. In addition, some devices will be fitted with a voltage/current data logger which will connect between the mains supply and the device, recording usage each time. This information will be recorded on the data logger memory and uploaded following the 3 months intervention period in order to cross reference against the compliance diary. This will act as a further robust mechanism to capture adherence to device use, with measurement of frequency of device use.

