### 5.2.2 Neuromuscular Electrical Stimulation Device (NMES)

The Neuromuscular Electrical Stimulation device (NMES) is recommended to the patient to be used once a day for 30 minutes, 7 days a week, for 12 weeks (84 days). The time of the day that the device is used is left up to the patient and usage is recorded via patient diaries.

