#### Summary scores

- Physical components score (PCS)
- Mental component score (MCS)

Imperial Clinical Trials Unit	STATISTICAL ANALYSIS PLAN	NESIC
-------------------------------	---------------------------	-------

- **Compliance Classification**

We have classified a participant as “compliant” if they have done at least 75% of the recommended target minutes for Device use, at least 75% of the recommended EA minutes performing exercises and attend at least 50% of SET sessions by the end of the treatment period. Then compliance can be dichotomised, coding “Yes, complied” if the patient complied with the recommended threshold treatment and “No” if patient did not comply. This classification is obtained by combining the compliance classification of the three instruments used to collect compliance information from each intervention (Device, SET and EA). Procedures for these classifications are outlined in Appendix 3 section 13.3).

For each treatment group, a patient is considered compliant if they are compliant for all of their assigned treatments. Therefore, for each of the treatment groups compliance is defined as follows:

- EA: compliant if done 75% or more of recommended level of EA (75% of minutes performing exercises recommended by centre)
- EA + SET: compliant if done 75% or more of recommended level of EA and attended 50% or more SET sessions held by centre.
- EA + NMES: compliant if done 75% or more of recommended level of EA and done 75% or more of recommended level of NMES usage
- EA + SET + NMES: compliant if done 75% or more of recommended level of EA, attended 50% or more SET sessions held by centre and done 75% or more of recommended level of NMES usage

These variables, excluding compliance classification, will be summarized at follow up time periods by treatment group using the ITT analysis set. Compliance classification will be summarised at the end of the intervention period. Summaries of continuous variables will be presented as mean and standard deviations if normally distributed, and as mean and inter-quartile ranges for skewed data. Categorical variables will be presented as frequencies and percentages.

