**Exercise Advice (EA) measured weekly from baseline at 3 months**

Recorded number of weeks of exercise reported in diary  
 Recorded total minutes of exercise at home per week

• Device experience questionnaire

A simple device use questionnaire will be administered by device users to report their subjective experience with the device. The questionnaire contains 6 questions:

- Overall, how easy did you find the device to use?
- Do you think the device helped to lessen the pain?
- Do you think you can walk further?
- Did you use the device as instructed?
- Do you think you could have used the device more often than you did?

Imperial Clinical Trials Unit	STATISTICAL ANALYSIS PLAN	NESIC
-------------------------------	---------------------------	-------

- Did you use the device beyond the 3 months treatment?
- Compliance Classification for each of SET, NMES and EA.

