**Table A2 Overview of the Neuromuscular electrical stimulation device (NMES)**

Minutes for session	Sessions per week	Number of weeks	Total of sessions	Total minutes
30	7	12	84	2520

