**Table A7 NMES Compliance Measurement**

Minutes for session	Sessions per week	Number of weeks	Total of sessions	Total minutes	75% of min
30	7	12	84	2520	1890

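### The SAP's single 1890-minute NMES compliance cut-off classes device patients with diabetes as compliant at 37.5%, not 75%, of the minimum use the protocol recommends for them

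*SAP*

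**What the plan says.** **Protocol.** Section 5.5.4 advises device patients in general to complete at least one 30-minute session a day, up to six. It then sets a higher minimum for one group: "Where patients are also diagnosed with diabetes, a minimum usage of two (2) x 30 minute sessions per day is recommended".

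**SAP, dose.** Section 13.3.3 says that "patients are recommended to use the device for 30 minutes a day for 12 weeks, for a total of 2520 minutes". Section 5.2.2 and Table A2 give the same once-daily regimen of 84 sessions. Table A7 has a single row: 2520 minutes in total, with 1890 minutes as the 75% mark. The SAP mentions no separate dose for patients with diabetes.

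**SAP, rule.** Section 7.2 requires "at least 75% of the recommended target minutes for Device use" for the device component, and for the composite "a patient is considered compliant if they are compliant for all of their assigned treatments". Section 7.4 lists "Compliance Classification for each of SET, NMES and EA" among the secondary endpoint variables. Tables 15 and 61 report the composite, by arm and by subgroup. Section 8.8.1 analyses the primary and secondary endpoints in compliers.

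**The concern.** The SAP defines device compliance relative to what was recommended, then fixes the recommendation at the general dose. For patients with diabetes the protocol's minimum is twice as high. Someone in that group averaging less than one full session a day is counted as adherent to a two-session regimen.

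These patients can be in the trial: diabetes is not an exclusion criterion, and SAP Table 8 has a row for it. Compliance is a listed secondary endpoint, and the composite decides who enters the 8.8.1 analysis. A wrong threshold therefore changes a reported classification and the membership of an analysis set. It is more than a gap in the description.

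**Working it through.** **Inputs**
- General dose: 30 min a day for 84 days (SAP 5.2.2, 13.3.3, Tables A2 and A7).
- Minimum for patients with diabetes: 2 × 30 = 60 min a day (protocol 5.5.4).
- Threshold: 75% of the recommended minutes (SAP 7.2).
- Planned sizes: 96 in the device arm, 48 in each device subgroup (protocol 3.2, Table 1).

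**Step 1. Reproduce the SAP figures.** 30 × 7 × 12 = 2520 min, and 0.75 × 2520 = 1890 min. Both match Table A7. The cut-off equals 1890/30 = 63 sessions, or 1890/84 = 22.5 min a day on average.

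**Step 2. Apply the same rule to the diabetes minimum.** 60 × 84 = 5040 min (168 sessions), and 0.75 × 5040 = 3780 min. That is 126 sessions, or 3780/84 = 45 min a day.

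**Step 3. Compare.**

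| Device use by a patient with diabetes | SAP target (2520) | Protocol minimum (5040) |
|---|---|---|
| 1890 min (SAP cut-off) | 75% | 37.5% |
| 2520 min (one session every day) | 100% | 50% |
| 3780 min | 150% | 75% |

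**Step 4. Sensitivity to the treatment window.** The 5040 figure combines the protocol's daily dose with the SAP's 84 days. If 3 months is instead taken as 90 to 92 days (an assumption), the minimum is 60 × 90 = 5400 to 60 × 92 = 5520 min. Then 1890 is 35.0% to 34.2% of it. The conclusion does not depend on the choice.

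**Step 5. Who changes class.** Only device-arm patients with diabetes and 1890 to 3779 min change on the NMES component. Each one moves an NMES-only proportion by 1/96 = 1.04 percentage points in the device arm, or 1/48 = 2.08 points in one device subgroup, at planned sizes. The composite moves by no more than that, because a patient must also meet the EA threshold and, where assigned, the SET threshold to have counted as compliant. The documents give neither diabetes prevalence nor usage data, so the total cannot be computed.

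**Step 6. What uses the cut-off.** The primary model (SAP 8.2) is fitted to the intention-to-treat set. The per-protocol set (SAP 6.2) depends on SET attendance and withdrawal. The CACE analysis in SAP 6.1 is triggered by SET uptake. Table 50 summarises raw device days, minutes and intensity. None of these uses 1890 minutes.

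**The case against.** **The SAP is consistent with itself.** Section 7.2 refers to Appendix 3 for the procedure, and Appendix 3 says 2520 minutes. This is true, but Appendix 3 presents that figure as what patients are recommended, and for patients with diabetes it is not what the protocol recommends.

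**A common floor can be defended.** One session a day is the general minimum, and where EA advice is a range the SAP takes the lower end (Southampton in Table A5: 1080 to 1800 min, cut-off 810 = 0.75 × 1080). However, that range is one piece of advice given to all patients at the centre. The diabetes dose is a separate, higher minimum for an identifiable group. The SAP also tailors EA and SET targets to each centre's advice and gives no reason for treating NMES differently. A justified common floor would be coherent, but it would have to be stated, and 7.2 could then no longer describe it as 75% of the recommendation for everyone.

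**Protocol 1.6.6 mentions one 30-minute treatment a day.** That describes the device's intended use in healthy individuals, not the trial dose.

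**The number affected may be small.** This stands. Peripheral neuropathy is an exclusion, which may reduce the number of patients with diabetes, and the composite has further conditions.

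**Some early patients may have been advised differently.** A reader might infer from the V3.0 entry in the protocol's revision summary that the diabetes dose was new at that version, and that the target should switch by protocol version. The entry records only a dosage clarification, and the documents give no approval or site implementation date for V3.0. Randomisation date alone cannot show which advice a patient received, so a version-based rule is not supported.

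**Conclusion.** The mismatch is definite and its size is exact: on the SAP's 84-day window, patients with diabetes are classed as NMES-compliant at 1890/5040 = 37.5% of their recommended minimum, where SAP 7.2 says 75%. No other section of the SAP corrects this. Measured against the protocol dose, the NMES compliance proportion under the SAP rule can only be equal or too high.

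The reach is limited to the NMES classification, the composite in Tables 15 and 61, and the 8.8.1 complier analysis. The number of patients affected is unknown.

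Two stronger readings are tempting and are not supported. The first is that the trial's main result is compromised; neither the primary intention-to-treat analysis nor the per-protocol analysis uses the cut-off. The second is that the complier estimate is biased in a known direction. Correcting the cut-off removes some low-use patients with diabetes from the device-arm compliers, but nothing in the documents shows how their walking distances compare with those of the compliers who remain.

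**What to change.** - In SAP 13.3.3, Table A2 and Table A7, add a row for device-arm patients with diabetes recorded at baseline: target 5040 min, cut-off 3780 min. Keep 2520 and 1890 min for all other device patients.
- Align SAP 5.2.2 with protocol 5.5.4 by stating both recommended minimums.
- Report the common 1890-minute classification, and the 8.8.1 analysis based on it, alongside as a sensitivity version. This also covers any early patients who were advised differently.

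**Cost.** SAP wording and a recode. Diabetes status (Table 8) and daily device minutes (SAP 7.4) are already collected, and the primary analysis does not change.

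**Downside.** The stricter cut-off applies only in the device arm and has no counterpart in control. The complier comparison is already non-randomised, and this may increase the imbalance in diabetes between its groups. Showing both versions lets the reader judge how much the choice matters.

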**Table A7 NMES Compliance Measurement**

Minutes for session	Sessions per week	Number of weeks	Total of sessions	Total minutes	75% of min
30	7	12	84	2520	1890
